2.3. Benefit/Risk Assessment

Based upon pre-clinical studies and clinical studies of prior MIs (GSK3532795 and GSK3640254) the major potential risks are GI intolerance (e.g. abdominal pain and diarrhoea), gastric toxicity (effects on parietal cells and chief cells), prolongation of QTc, skin and subcutaneous tissue disorders (maculopapular rash) and neuropsychiatric safety. A preclinical toxicity finding observed microscopically in stomach (single-cell necrosis of parietal cells) was seen in animals at exposures of VH3739937 that will be tested in this study, however the microscopic finding was minimal and reversible in animals. As noted in Section [2.3.1](#), the GLP hERG invitro assay showed an atypical response (inhibition (~47%) at 2.306 - 0.231 equivalent to 0.073 µg/mL. This is consistent with the other non-clinical CV data which demonstrated high margin (see Section [2.3.1](#). for further detail).

In a single-dose study of respiratory function in telemetered rats, VH3739937 resulted in mild reductions in respiratory rate and increased reversible pulmonary resistance. The protocol includes frequent monitoring of vital signs including respiratory rate and brief physical examinations including respiratory examination.

The protocol will exclude potential participants from the study with any pre-existing psychiatric condition or positive (abnormal) response confirmed by the investigator on a clinician (or qualified designee) administered CSSRS. The CSSRS assessment will also be administered by a clinician (or qualified designee) during the on-treatment portion of the MAD only.

Thus, to ensure the overall safety of participants (including, but not limited to, the risk of GI intolerance, QTc prolongation, skin disorders and neuropsychiatric safety), this clinical trial will include healthy adults who will be actively monitored by receiving frequent clinical, ECG, and laboratory evaluations during their participation in the trial.

In addition, consistent with Sponsor guidance for early phase studies, this study will be conducted in a hospital-based clinical research unit with prior experience with first-time-in-human-trials, sufficient overnight facilities and immediate emergency care capabilities.

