3. OBJECTIVES AND ENDPOINTS

Objectives	Endpoints
Primary	

 To investigate the safety and tolerability of VH3739937 following single, repeated daily, and weekly oral administration in healthy participants (Part 1 & 2) To assess the safety and tolerability of VH3739937 following single oral administration in healthy participants under fasted or fed (moderate calorie and fat) conditions (Part 3) To evaluate the relative bioavailability (RBA) of GSK3739937 powder-in-bottle (PiB) versus GSK3739937 Tablet and the effect of food on the PK of GSK3739937 Tablets and GSK3739937 PiB (Part 3) 	
VH3739937 safety parameters:
 
 Adverse events; post baseline values and changes over time of clinical laboratory evaluations (haematology, clinical chemistry, urinalysis), vital signs, and ECG parameters from pre-dose values (Part 1, 2 & 3) Derived PK parameters for VH3739937 Part 3 (single dose): $AUC_{(0-24)}$, $AUC_{(0-\infty)}$, C_{max}
Secondary	

 To describe the PK profile of VH3739937 following single (Part 1 & 3), repeated 	Derived PK parameters for VH3739937:

Objectives	Endpoints
daily and weekly (Part 2) oral administration in healthy participants	
 Part 1 (single dose): $AUC_{(0-24)}$, $AUC_{(0-t)}$, $AUC_{(0-\infty)}$, C_{max}, C_{24}, t_{max}, t_{lag}, $t_{1/2}$, C_{last}, t_{last}, CL/F Part 2 (repeated once daily [QD] dose): 
 Day 1: $AUC_{(0-24)}$, C_{max}, C_{24}, t_{max}, t_{lag} Day 14 (Cohorts 3 and 4): $AUC_{(0-\tau)}$, C_{max}, C_{τ}, t_{max}, $t_{1/2}$, and CL/F Day 18 (Cohort 5): $AUC_{(0-\tau)}$, C_{max}, C_{τ}, t_{max}, $t_{1/2}$, and CL/F Part 2 (repeated once weekly [QW] dose): 
 Day 1 (Cohort 6): $AUC_{(0-168)}$, C_{max}, C_{168}, t_{max}, t_{lag} Day 15 (Cohort 6): $AUC_{(0-t)}$, C_{max}, C_t, t_{max}, $t_{1/2}$, and CL/F Part 3 (single dose): C_{24}, t_{max}, t_{lag}, $t_{1/2}$, C_{last}, t_{last}, CL/F

 To examine dose proportionality following single and repeated doses of VH3739937 (Part 1 & 2) 	
Derived PK parameters for VH3739937:
 
 Part 1 (single dose): $AUC_{(0-\infty)}$, C_{max}. Part 2 (repeated dose): $AUC_{(0-\tau)}$, C_{max}, C_{τ}

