8.1.2. Vital Signs

- Single oral temperature, pulse rate, respiratory rate and blood pressure will be assessed.
- All blood pressure and pulse measurements will be assessed in semi-supine position with a completely automated device. Manual techniques will be used only if an automated device is not available.
- Blood pressure and pulse measurements will be preceded by at least 5 minutes of rest for the participant in a quiet setting without distractions (e.g., television, cell phones).
- Vital signs (to be taken before blood collection for laboratory tests) will consist of 1 pulse and 3 blood pressure measurements (3 consecutive blood pressure readings will be recorded at intervals of at least 1 minute). In addition, temperature will be monitored daily during study participation.
- Additional details can be found in the SRM.

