13.8.4. Vital Signs

Vital Sign Parameter (Absolute)	Units	Clinical Concern Range	
		Lower	Upper
Systolic Blood Pressure	mmHg	< 85	> 160
Diastolic Blood Pressure	mmHg	< 45	> 100
Heart Rate	bpm	< 40	> 110

Vital Sign Parameter (Change from Baseline)	Units	Clinical Concern Range	
		Decrease	Increase
Systolic Blood Pressure	mmHg	≥ 40	≥ 40
Diastolic Blood Pressure	mmHg	≥ 20	≥ 20
Heart Rate	bpm	≥ 30	≥ 30

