3.27.	Safety	UR1	Summary of Worst Case Urinalysis Results Post-Baseline Relative to Baseline – Part 2	ICH E3, For discrete or character values only	SAC [1], HL

Safety: Tables					
No.	Population	GSK Standard/ Example Shell	Title	Programming Notes	Deliverable [Priority]
3.28.	Safety	UR1	Summary of Worst Case Urinalysis Results Post-Baseline Relative to Baseline – Part 3	ICH E3, For discrete or character values only	SAC [1], HL
ECG					
3.29.	Safety	EG1	Summary of ECG Findings - Part 1	GSK Statistical Display Standard	SAC [1]
3.30.	Safety	EG1	Summary of ECG Findings – Part 2	GSK Statistical Display Standard	SAC [1]
3.31.	Safety	EG1	Summary of ECG Findings – Part 3	GSK Statistical Display Standard	SAC [1]
3.32.	Safety	EG10A	Summary of Maximum QTc Values Post-Baseline Relative to Baseline by Category	GSK Statistical Display Standard, ICH E14, page by part	SAC [1], HL
3.33.	Safety	EG2	Summary of Change from Baseline in ECG Values by Visit	GSK Statistical Display Standard, page by part	SAC [1]
3.34.	Safety	EG11A	Summary of Maximum Increase in QTc Values Post-Baseline Relative to Baseline by Category	GSK Statistical Display Standard, page by part	SAC [1], HL
Vital Signs					
3.35.	Safety	VS3A	Summary of Vital Sign Shifts from Baseline Relative to Potential Clinical Importance (PCI) Criteria	GSK Statistical Display Standard, page by part	SAC [1], HL

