13.10.9. Non-ICH Listings

Non-ICH: Listings					
No.	Population	GSK Standard / Example Shell	Title	Programming Notes	Deliverable [Priority]
Subject Disposition					
17.	Screened	ES7	Listing of Reasons for Screen Failure	Journal Guidelines	SAC [1]
18.	Safety	TA1xo	Listing of Planned and Actual Treatments	GSK Statistical Display Standard	SAC [1]
19.	Enrolled	PAN5	Country Level Listing of Start Dates of COVID-19 Pandemic Measures		SAC [1]
Protocol Deviation					
20.	Safety	DV2xo	Listing of All Non-Important COVID-19 Related Protocol Deviations		SAC [1]
21.	Safety	PAN7	Listing of All Subjects with Visits and Assessments Impacted by COVID-19 Pandemic		SAC [1]
Prior and Concomitant Medications and Medical History					
22.	Safety	CM10xo	Listing of Concomitant Medications	GSK Statistical Display Standard, page by part	SAC [1]
23.	Safety	MH2xo	Listing of Medical Conditions	Page by Part	SAC [1]
Adverse Events					
24.	Safety	PAN12	Listing of COVID-19 Assessments and Symptom Assessments for Subjects with COVID-19 Adverse Events		SAC [1]

CONFIDENTIAL

212548

Non-ICH: Listings					
No.	Population	GSK Standard / Example Shell	Title	Programming Notes	Deliverable [Priority]
ECG					
25.	Safety	EG3xo	Listing of All ECG Values for Subjects with Any Value of Potential Clinical Importance		SAC [1]
Vital Signs					
26.	Safety	VS4xo	Listing of All Vital Signs for Subjects with any Value of Potential Clinical Importance		SAC [1]
Laboratory					
27.	Safety	LB14	Listing of Laboratory Data with Character Results		SAC [1]
CSSRS					
28.	Safety	CSSRS4	Listing of C-SSRS Suicidal Ideation and Behaviour Data	Include only subjects with at least one positive (Yes) response	SAC [1]
PK Endpoints					
29.	PK	PK07xo	Listing of VH3739937 Plasma Pharmacokinetic Concentration-Time Data Treatment		SAC [1]
30.	PK	PK13xo	Listing of Derived VH3739937 Plasma Pharmacokinetic Parameters by Treatment		SAC [1]
Hepatobiliary (Liver):					
31.	Safety	LIVER5	Listing of Liver Monitoring/Stopping Event Reporting	GSK Hepatic Safety Panel	SAC [1]
32.	Safety	LIVER15	Liver Stopping Event Profile	GSK Hepatic Safety Panel	SAC [1]
33.	Safety	LIVER13	Listing of Subjects Meeting Hepatobiliary Laboratory Criteria Post-Baseline		SAC [1]
34.	Safety	MH2xo	Listing of Medical Conditions for Subjects with Liver Stopping Events	Optional listing	SAC [1]

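### Vital-sign values and changes over time are part of the primary safety endpoint, but the SAP plans no table that summarises them by time point, and respiratory rate and temperature have no criterion for the one vital-sign table planned.

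*SAP*

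**What the plan says.** The primary safety endpoint in Parts 1, 2 and 3 covers adverse events and "post baseline values and changes over time of clinical laboratory evaluations (haematology, clinical chemistry, urinalysis), vital signs, and ECG parameters from pre-dose values" (Protocol section 3, repeated in SAP 2.2). On what is measured, Protocol 8.1.2 states: "Single oral temperature, pulse rate, respiratory rate and blood pressure will be assessed".

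Protocol 2.3 gives a reason to look at one of these measures. In a single-dose study in telemetered rats, "VH3739937 resulted in mild reductions in respiratory rate and increased reversible pulmonary resistance". The protocol's response follows directly: "The protocol includes frequent monitoring of vital signs including respiratory rate and brief physical examinations including respiratory examination".

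On reporting, Protocol 9.6 commits to listings and to summaries broken down by part, treatment, day and time, with n, mean, SD, median and range for continuous variables unless stated otherwise. SAP 7 says the primary safety data will be tabulated and described. SAP 7.3 places vital signs under company data standards and refers to Appendix 10 for the planned displays. Appendix 10 contains two vital-sign displays:

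- Table 3.35 (SAP 13.10.5): "Summary of Vital Sign Shifts from Baseline Relative to Potential Clinical Importance (PCI) Criteria".
- Listing 26 (SAP 13.10.9): "Listing of All Vital Signs for Subjects with any Value of Potential Clinical Importance".

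SAP 13.8.4 supplies the PCI limits. SAP 2.1 declares no departure from the analysis planned in the protocol.

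**The concern.** A table of threshold crossings does not report values or changes over time. It says how many participants crossed a limit, not what the mean or spread was at each time point or how far it moved from baseline. If the SAP is followed as written, one named component of the primary safety endpoint has no by-visit summary by treatment. Two collected measures are worse placed, because they have no limit to cross.

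Respiratory rate matters most, because the protocol ties it to a nonclinical finding. A reader of the study report who wanted to know whether mean respiratory rate moved with dose would find no planned table giving the answer. The same holds for a modest mean shift in blood pressure or pulse at a particular post-dose time.

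**Working it through.** No power or sample-size figure is involved. The check compares what the endpoint requires and what is collected with what is planned for display.

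**1. Is the display list complete?** SAP 13.10.1 gives the safety tables as 3.1 to 3.35 and safety figures as not applicable. Counting the rows of 13.10.5:

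- adverse events, 3.1–3.21: 21 tables
- laboratory, 3.22–3.28: 7 tables
- ECG, 3.29–3.34: 6 tables
- vital signs, 3.35: 1 table

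21 + 7 + 6 + 1 = 35, which matches the stated range. No vital-sign table has been lost in the text.

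**2. Which continuous components of the endpoint have a change-from-baseline table?**

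| Component | Change-from-baseline table |
|---|---|
| Clinical chemistry | 3.22 |
| Haematology | 3.24 |
| ECG values | 3.33, by visit |
| Vital signs | none |

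The text follows the same pattern. SAP 7.2 says chemistry and haematology values and changes will be summarised by visit and treatment. SAP 7.3 makes no such statement for vital signs and mentions only worst-case post-baseline results. SAP 5.2 defines a vital-sign baseline, but no planned table reports mean change from it.

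**3. Which collected measures have a PCI limit in SAP 13.8.4?**

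| Measure | Absolute limits | Change limit, either direction |
|---|---|---|
| Systolic BP | <85 or >160 mmHg | ≥40 mmHg |
| Diastolic BP | <45 or >100 mmHg | ≥20 mmHg |
| Heart rate | <40 or >110 bpm | ≥30 bpm |
| Respiratory rate | none | none |
| Temperature | none | none |

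Three of five measures have limits. The other two have no criterion for Table 3.35, and neither can bring a participant into Listing 26. Their values could appear in that listing only for someone who qualified on blood pressure or heart rate, and a listing is not a summary.

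**4. How sensitive is the shift table for the measures that do have limits?** This needs an SD of change, which the documents do not give. The SDs and mean rises below are assumptions. For a mean rise m and SD s at one reading, the chance that one participant reaches limit L is p = 1 − Φ((L − m)/s), and for any of the 6 active participants in a Part 1 period it is 1 − (1 − p)^6.

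- Systolic, L = 40, m = 10, s = 10: z = 3, p = 0.00135, any of 6 = 0.8%.
- Systolic, L = 40, m = 20, s = 10: z = 2, p = 0.0228, any of 6 = 13%.
- Diastolic, L = 20, m = 10, s = 8: z = 1.25, p = 0.1056, any of 6 = 49%.

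These are single-reading figures. Participants are measured repeatedly, so if the rise were present at every reading, the chance of at least one crossing would be higher. A table of change from baseline would instead show the mean itself: for s = 10 and n = 6 its standard error is 10/√6 = 4.1 mmHg.

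**The case against.** The strongest defence is that the general commitments already cover this. Protocol 9.6 calls for summaries by treatment, day and time, SAP 7 promises descriptive tables, SAP 7.3 invokes company standards, and SAP 2.1 declares no deviation. On that view the missing table is an oversight in a list. This is fair as a description of intent. A reader might infer that the sponsor decided not to summarise vital signs, and the documents do not support that. The commitments do not cure the gap, however, because SAP 7.3 refers to Appendix 10 for the displays and Appendix 10 names no such table. The company layout for Table 3.35 is not in the documents, so its exact content cannot be checked.

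Two further objections limit how far the point can be taken, and both stand.

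- A reader might infer that a respiratory effect would go unseen. Protocol 10.3.1 makes a vital-sign abnormality that the investigator judges clinically significant an adverse event, so it would enter the adverse-event tables. Vital signs are also among the data the Dose Escalation Committee reviews (Protocol 4.3.6). What is lost is the estimate of a group-level shift below that threshold, not the protection of participants.
- A reader might infer from the 40 mmHg systolic limit that Table 3.35 would probably be empty even with a real effect. That rests on one measure, one direction and one reading. The diastolic calculation above gives about an even chance of a crossing at a 10 mmHg mean rise. Heart-rate and absolute limits, and the other dose levels, add more.

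It could also be said that respiratory rate and temperature need PCI limits of their own. The endpoint does not require them once the values are summarised, and the documents give no basis for a cut-off.

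**Conclusion.** The point holds as a mismatch between the primary endpoint and the list of displays. None of the 35 safety tables is titled as a summary of vital-sign values or change from baseline by time point, and two of the five collected measures have no criterion for the only vital-sign table. The planned tables would therefore give no estimate of a group-level shift in respiratory rate or temperature, or of a mean blood-pressure or pulse shift at a time point.

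Large blood-pressure and heart-rate changes would still be counted against the PCI limits. The finding about which tables exist needs no statistical assumption. It rests on the table titles and on SAP 7.3 deferring to Appendix 10. The crossing probabilities depend on assumed SDs and show only that a shift table cannot stand in for a mean. This should be corrected before the final displays are produced. It does not affect the design or conduct of the study.

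**What to change.** Add one table to SAP 13.10.5, for example as 3.36: observed values and change from baseline by visit or time point and treatment, paged by part as Table 3.33 is, for systolic BP, diastolic BP, pulse, respiratory rate and temperature. Use the baselines already defined in SAP 5.2, add a sentence to SAP 7.3 naming the summary, and extend the table range in SAP 13.10.1. If the sponsor prefers not to add it, SAP 2.1 should state and justify the omission against Protocol section 3 and 9.6.

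The cost is the programming and checking of one descriptive table and three small text edits. The data are already collected, and Table 3.35, Listing 26 and the limits in 13.8.4 can stay as they are.

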13.10.6. Pharmacokinetic Tables

Pharmacokinetic: Tables					
No.	Population	GSK Standard / Example Shell	Title	Programming Notes	Deliverable [Priority]
PK Concentration					
4.1.	PK	PK01	Summary of VH3739937 Plasma Pharmacokinetic Concentration (ng/mL) -Time Data by Treatment	Page by part	SAC [1]
4.2.	PK	PK03	Summary of Derived VH3739937 Plasma Pharmacokinetic Parameters by Treatment		SAC [1],HL
4.3.	PK	PK05	Summary of Log-Transformed Derived VH3739937 Plasma PK Parameters by Treatment		SAC [1],HL
Dose Proportionality, Accumulation, and Steady State					
4.4.	PK	PK_T1	Summary Results of Single Dose Proportionality Assessment Using Power Model – Part 1	Stats output, Non-Standard Shell PK_T1 PK parameters: AUC(0-inf), AUC(0-t), Cmax	SAC
4.5.	PK	PK_T1	Summary Results of Multiple Dose Proportionality Assessment Using Power Model – Part 2	Stats output Non-standard shell PK_T1 PK parameters: AUC(0-inf), AUC(0- τ), Cmax	SAC
4.6.	PK	PK_T2	Summary Results of Steady State VH3739937 Concentrations Assessment – Part 2	Stats output Non-standard shell PK_T2 Use up to day 14 for cohort 3 and 4 and day 18 for cohort 5.	SAC

Pharmacokinetic: Tables					
No.	Population	GSK Standard / Example Shell	Title	Programming Notes	Deliverable [Priority]
				Add footnote: Ctrough was collected on days 2,3,4,6,8, 10,11,12,13,14,15 for cohort 3 and 4 and days 2,3,4,6,8, 10,11,12,13,14,15, 16, 17,18 for cohort 5. Use C_{τ} to determine steady state for daily dosing MAD. See example from Table 4.13 from study 207187	
4.7.	PK	PK_T3	Summary Results of VH3739937 PK Parameter Treatment Comparisons Predicted Accumulation Ratio- Part 1	Stats output, Non-Standard Shell at end of RAP Non-standard shell PK_T3	SAC
4.8.	PK	PK_T4	Summary Results of VH3739937 PK Parameter Treatment Comparisons Accumulation Ratio- Part 2	Stats output, Non-standard shell PK_T4 Add footnote: In Cohort 6, since sampling at 168 hrs (7 days) post 3 rd dose was not collected, it will be approximated by 192 hrs post dose.	SAC
Relative Bioavailability/Food Effect					
4.9.	PK	PK_T5	Summary of Result of Plasma VH3739937 Pharmacokinetic Parameter Treatment Comparisons for Relative Bioavailability	Stats output	SAC [1], HL

Pharmacokinetic: Tables					
No.	Population	GSK Standard / Example Shell	Title	Programming Notes	Deliverable [Priority]
				PK Parameters: $AUC_{(0-24)}$, $AUC_{(0-\infty)}$, and C_{max} Ratio: Test/Reference (Tablet/PiB) See study mid208131 Table 4.4 for reference Non-standard shell PK_T5	
4.10.	PK	PK_T5	Summary of Result of Plasma VH3739937 Pharmacokinetic Parameter Treatment Comparisons for Food Effect	Stats output PK Parameters: $AUC_{(0-24)}$, $AUC_{(0-\infty)}$, and C_{max} Ratio: Test/Reference (Fed Tablet/Fasted Tablet). See study mid208131 Table 4.4 for reference Non-standard shell PK_T5	SAC [1], HL

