Overall Rationale for the Amendment:

Updates made following acquisition of clinical pharmacology data in Part 1, the Single Ascending Dose (SAD) 10 mg, 30 mg, 80 mg, 160 mg, 320 mg and 640mg treatment periods and Multiple Ascending Dose (MAD) Cohort 3; 25 mg to:

- extend the period of post dosing assessment to include outpatient visits in the study;
- include a higher dose SAD treatment period (800 mg);
- revise the duration of dosing in MAD Cohort 5 (100 mg); and
- inclusion of an additional MAD Cohort 6 (500 mg) to evaluate weekly oral dosing.

Part 3 of the study was included to evaluate the relative bioavailability (RBA) of VH3739937 when administered as GSK3739937 powder-in-a-bottle (PiB) or as GSK3739937 100 mg Tablet under fasted and fed (moderate fat) conditions.

Section # and Name	Description of Change	Brief Rationale
1.1 Synopsis	Updates supporting conduct of additional 800 mg SAD treatment period, reduced dosing duration of MAD Cohort 5, weekly MAD Cohort 6 and Relative Bioavailability (RBA) and Food Effect (FE) cohort. Updated text regarding use of GSK3739937 (also known as VH3739937).	Revisions and updates based on observed longer PK half-life and observed safety data through to 640 mg SAD dose period and MAD Cohort 3. Sponsor decision to use GSK3739937 (also known as VH3739937) where indicated to further clarify Sponsor asset.
1.2 Schedule of Activities (SOA)	All SOA updated to include additional outpatient visits and assessments. SAD SOA revised to include additional treatment period. Update to support MAD Cohort 5 SOA reduced dosing duration. Addition of SOA for weekly MAD cohort and RBA and FE cohort	Revisions and updates to SOA were based on emerging PK data indicating longer PK half-life than anticipated and following review of emerging safety data and to support operational efficiencies
2.1 Study Rationale	Updates supporting conduct of additional 800 mg SAD treatment period, reduced dosing duration of MAD Cohort 5, weekly MAD cohort and Relative Bioavailability (RBA) and Food Effect (FE) cohort.	Revisions and update based on observed longer PK half-life and following review of emerging safety data

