Plasma PK Sampling			X		X	X	X	X	X	X	X	X	X	X	X	X	X	X	X	In Cohort 1, 4mL of blood will be collected for analysis at each timepoint. In Cohort 2, 2 mL of blood	

Procedure	Day -2	Day -1	Day 1 (Hours)													Day 2 (24 h)	Day 3 (48 h)	Day 4 (72 h)	Day 5 (96 h)	Day 6 (120 h)	Notes Hours (h) relate to PK sampling post last dose
			Pre- dose	0	1	2	3	4	5	6	7	8	9	10	12	16					
																					will be collected at each visit. For further detail, see Section 8.4.
Urine PK Sampling			X																		Pre-dose urine can be collected up to 3.5 h pre- dose. Afterward urine will be collected over 24 h collection periods as follows: 0-24 h, 24-48 h, 48 – 72 h, 72 – 96 h in Cohort 2 Period 3 only. For further detail, see Section 8.4.
SAE Review																					All SAEs will be collected from screening until follow up visit

Procedure	Day -2	Day -1	Day 1 (Hours)													Day 2 (24 h)	Day 3 (48 h)	Day 4 (72 h)	Day 5 (96 h)	Day 6 (120 h)	Notes Hours (h) relate to PK sampling post last dose
	Pre- dose	0	1	2	3	4	5	6	7	8	9	10	12	16							
AE Review			<=====													>=====			All AEs will be collected from first dose until follow up visit		
Concomitant Medication Review			<=====													>=====					

Table 2 continued Part 1 SAD Cohorts 1 and 2 Periods 1 through 4 – Outpatient Visit

Procedure	Day			Notes Hours (h) relate to PK sampling post last dose
	9 (192 h)	12 (264 h)	16 (360 h)	
Outpatient Visit	X	X	X	
Brief Physical Exam	X	X	X	Brief physical examinations may be made full and laboratory procedures may be repeated if needed at the discretion of the PI.
Vital signs	X	X	X	For further detail, see Section 8.1.2
12-lead safety ECGs	X	X	X	For further detail, see Section 8.1.4
Haematology/Chemistry/Urine tests	X	X	X	For further detail, see Section Appendix 2
Plasma PK Sampling	X	X	X	In Cohort 1, 4mL of blood will be collected for analysis at each timepoint. In Cohort 2, 2 mL of blood will be collected at each visit. For further detail, see Section 8.4.
Urine PK Sampling	X	X	X	For Cohort 2 Period 3 only, fresh spot urine sample collection at each visit. Please see SRM for further detail.
SAE/AE Review	<=====>			All SAEs will be collected from screening until follow up visit; All AEs will be collected from first dose until follow up visit
Concomitant Medication Review	<=====>			

Table 3 Part 2 Multiple ascending dose (MAD) Cohorts 3 and 4: Study Intervention - In Unit Duration

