This dose/exposure range in healthy participants is clinically reasonable based upon the preclinical profile of VH3739937 and the clinical profile of prior MIs (GSK3640254 and GSK3532795), and the planned inpatient and outpatient evaluation for potential treatment emergent risks: including QT prolongation, GI intolerance and neuropsychiatric safety – which will be frequently monitored in this limited dosing duration setting. The preliminary data observed to date in this study (212548) through 640 mg in the SAD and 25 mg QD for 14 days in the MAD have not highlighted a significant safety concern. Phase 1-2a studies with GSK3640254 have not evaluated for the presence of gastric toxicity in humans; thus, it is unclear if any of the GI AEs observed in any clinical trial were representative of, associated with, or resulted from gastric toxicity (if present). However, a currently active Phase 2b study of GSK3640254 includes a sub-study to assess the potential for GI toxicity.

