
 ● To examine dose proportionality following single and repeated doses of VH3739937 (Part 1 & 2), as data permits 	
Derived PK parameters for VH3739937, as data permits:
 
 ● Part 1 (single dose): $AUC_{(0-\infty)}$, C_{max}. ● Part 2 (repeated dose): $AUC_{(0-\tau)}$, C_{max}, $C\tau$

 ● To predict the accumulation from single dose data (Part 1) and assess accumulation of VH3739937 after repeat doses (Part 2 at steady state), as data permits 	
Accumulation indices for PK parameters for VH3739937, as data permits:
 
 ● Part 1 (single dose): predicted accumulation ratio R_p based on AUC ● Part 2 (repeated dose): observed accumulation ratios: $RAUC(0-\tau)$, $R(C_{max})$, $R(C\tau)$

 ● To assess time to steady-state of VH3739937 (Part 2) 	
Derived PK parameters for VH3739937, as data permits:
 
 ● Part 2 (repeated dose): 
 ○ Cohorts 3 and 4: Pre-dose concentrations on Day 2-14 ○ Cohort 5: Pre-dose concentrations on Day 2-18
Exploratory Objectives	Exploratory Endpoints

 ● To assess the exposure response relationship between VH3739937 and safety parameter, including QTcF following single and repeated administration (Part 1 & 2) 	
 ● Change-from-baseline QTcF ($\Delta QTcF$)

Objectives	Endpoints

• To collect plasma and urine samples for analysis of metabolites of VH3739937	
• Metabolites of VH3739937 in plasma and urine. The analyses will be conducted and reported separately from this protocol.

• To characterize renal excretion of VH3739937, as data permits	
• Urinary recovery of VH3739937 ($Ae[0-x]$), $Ae[0-\tau]$ and $Ae[0-t]$) and renal clearance (CLR)

• To collect duodenal bile for analysis of metabolites of VH3739937 (Part 2, Cohort 5 only)	
• Metabolites of VH3739937 in duodenal bile. The analyses will be conducted and reported separately from this protocol

- Note: The exploratory endpoints may be analyzed once VH3739937 clinical development continues.

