8.1.1.2. Derived Pharmacokinetic Parameters

Pharmacokinetic parameters will be calculated by standard non-compartmental analysis according to current working practices and using the currently supported version of WinNonlin. All calculations of non-compartmental parameters will be based on actual sampling times. Pharmacokinetic parameters listed will be determined from the plasma concentration-time data, as data permits.

Parameter	Parameter Description
AUC(0-inf)	Area under the concentration-time curve extrapolated to infinity will be calculated as: AUC = AUC(0-t) + C(t) / lambda_z
AUC(0-t)	Area under the concentration-time curve from time zero to the time of the last quantifiable concentration (C(t)) will be calculated using the linear trapezoidal rule for each incremental trapezoid and the log trapezoidal rule for each decremental trapezoid.
AUC(0-24)	Area under the plasma concentration time curve from zero to 24 hrs
AUC(0-168)	Area under the plasma concentration time curve from zero to 168 hrs
AUC(0- τ)	Area under the curve (Area under the plasma drug concentration-time curve from pre-dose to the end of the dosing interval at steady state)
%AUCex	The percentage of AUC (0-inf) obtained by extrapolation (%AUCex) will be calculated as: [AUC(0-inf) – AUC(0-t)] / AUC(0-inf) x 100
C _{max}	Maximum observed concentration, determined directly from the concentration-time data.
C ₂₄	Concentration at 24 hours post-dose
C ₁₆₈	Concentration at 168 hours post-dose
C _{last}	Last quantifiable concentration

Parameter	Parameter Description
$C\tau$	Pre-dose (trough) concentration at the end of the dosing interval
t_{max}	Time to reach C_{max} , determined directly from the concentration-time data.
$t_{1/2}$	Apparent terminal half-life will be calculated as: $t_{1/2} = \ln 2 / \lambda_{z}$
t_{lag}	Absorption lag time
t_{last}	Time of last quantifiable concentration
CL/F	Apparent oral clearance

NOTES:

- Additional parameters may be included as required.

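### SAP Table 4.4 fits the Part 1 power model to AUC(0-t), which depends on how long each dose level was sampled; an AUC to a common time should replace it

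*SAP*

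**What the plan says.** The programming note for SAP Table 4.4 (section 13.10.6) sets the inputs to the Part 1 power model as "PK parameters: AUC(0-inf), AUC(0-t), Cmax". The objective it serves is in SAP 2.2: "To examine dose proportionality following single and repeated doses of VH3739937 (Part 1 & 2), as data permits". The Part 1 endpoints beside that objective, there and in protocol section 3, are AUC(0-inf) and Cmax. AUC(0-t) is listed for Part 1 only as a descriptive PK-profile parameter.

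SAP 8.1.1.2 ends AUC(0-t) at the last quantifiable concentration. It defines AUC(0-inf) by adding the tail, "AUC = AUC(0-t) + C(t) / lambda_z", and also provides that "The percentage of AUC (0-inf) obtained by extrapolation (%AUCex) will be calculated as" the extrapolated area over the total.

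On sampling, the first purpose that Amendment 02 gives is to "extend the period of post dosing assessment to include outpatient visits in the study". It says the updates followed acquisition of data from the 10, 30, 80, 160, 320 and 640 mg single-dose periods and the 25 mg repeat-dose cohort. Protocol 4.2 likewise treats those data as in hand: "The preliminary data observed to date in this study (212548) through 640 mg in the SAD and 25 mg QD for 14 days". The current schedule (protocol 1.2) samples in the unit to 120 h. It then adds 192, 264 and 360 h under the title "Table 2 continued Part 1 SAD Cohorts 1 and 2 Periods 1 through 4 – Outpatient Visit".

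**The concern.** An AUC that stops at the last sample can be compared across doses only if every dose is followed for a similar time, or if sampling is long enough for the missing tail to be negligible. With a half-life of about 90 h, a profile that ends at 120 h covers only 1.3 half-lives. If the outpatient samples exist for some dose levels and not others, the levels without them have truncated AUC(0-t) values. If those are the lower doses, the power model reads the difference in follow-up as part of the dose slope.

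Single-dose proportionality is a secondary objective. At stake is a reported slope and 95% credible interval that reflect the sampling calendar as well as the drug. The SAP has no step that checks for this or corrects it.

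**Working it through.** **Inputs**
- Half-life about 90 h, with stated accumulation of about 6-fold daily and 1.3-fold weekly (protocol 4.1).
- Linear one-compartment model (protocol 2.2.1).
- Doses 10, 30, 80, 160, 320, 640 and 800 mg, with 6 active participants per level (protocol 4.1; SAP 5.1).
- Late samples at 192, 264 and 360 h (protocol 1.2).
- Assumed: the earlier stop time T (not in the documents), and a total CV of 25, 35 or 50%.

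**1. Reproduce the plan's own figure.** Accumulation = 1/(1 − 2^(−τ/90)). For τ = 24 h this is 5.93, matching about 6. For τ = 168 h it is 1.38 against the stated 1.3. That gap does not affect this point.

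**2. Share of AUC(0-inf) captured by time T**, ignoring the short absorption phase: F(T) = 1 − 2^(−T/90).
- F(120) = 0.603, so about 40% is extrapolated.
- F(360) = 0.9375, so about 6% is extrapolated.
- Ratio = 0.9375/0.603 = 1.55. With an assumed absorption rate of 0.3/h it is 1.58. For half-lives from 70 to 120 h it runs from 1.40 to 1.75.

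**3. Shift in the power-model slope.** With x the centred log dose, Sxx = 15.66, x(800) = 1.817 and x(640) = 1.594. The shift is Σ x·ln(ratio)/Sxx over the levels sampled to 360 h. At T = 120 h, ln(1.554) = 0.441:
- only 800 mg late: 1.817 × 0.441/15.66 = +0.051
- 640 and 800 mg late: (1.817 + 1.594) × 0.441/15.66 = +0.096
- 320 mg late as well: +0.121

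Across other stop times:

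| Earlier stop | AUC(0-360)/AUC(0-T) | Shift, 800 mg late | Shift, 640 and 800 mg late |
|---|---|---|---|
| 72 h | 2.20 | +0.09 | +0.17 |
| 96 h | 1.79 | +0.07 | +0.13 |
| 120 h | 1.55 | +0.05 | +0.10 |
| 192 h | 1.21 | +0.02 | +0.04 |
| 264 h | 1.08 | +0.01 | +0.02 |
| 360 h | 1.00 | 0 | 0 |

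**4. Precision of the slope.** Half-width ≈ 1.96·√ln(1+CV²)/√(6 × 15.66), treating the 42 observations as independent. This gives 0.050, 0.069 and 0.096 at CVs of 25, 35 and 50%. The crossover makes it approximate.

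**5. Direction.** Protocol Table 11 projects a median daily AUC of 22.7 at 50 mg and 39.8 at 100 mg, which implies a slope of ln(39.8/22.7)/ln 2 = 0.81. A shift of +0.05 to +0.10 would move such a slope to 0.86 to 0.91, closer to 1. A true slope of 1 would instead read as 1.05 to 1.10.

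**The case against.** The strongest reply is that unequal sampling is inferred, not documented. The current schedule gives 192 to 360 h for Periods 1 through 4. Escalation in Part 1 calls for PK through Day 16. Spot urine at the outpatient visits is assigned to Cohort 2 Period 3, the 640 mg period. Protocol 1.2 also lets time points be added without an amendment. All of this stands, and it means 640 mg, and perhaps other levels, may have late samples. It does not restore comparability unless every level has them, and adding 640 mg to the late group raises the shift from +0.05 to +0.10. On the other side, the amendment's stated sequence and the original half-life expectation of about 24 h (protocol 4.3.1, which makes 120 h five half-lives) favour a shorter early schedule. SAP 2.3 also still describes escalation on at least 24 hours of data. That differs from the protocol and must be reconciled in any case.

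Second, the declared endpoints are not exposed in the same way. Cmax is unaffected. AUC(0-inf) includes the tail, so a reader who infers that it carries the 1.55-fold shift would be wrong; a shorter profile makes it depend more on extrapolation.

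Third, protocol 9.4.4 leaves the choice of parameters for the power model open, so adding AUC(0-t) is not a breach. That is fair. The objection to AUC(0-t) is its dependence on schedule.

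Fourth, a reader might infer that %AUCex is computed and then ignored. It is not: SAP 8.1.1.2 lists it and summarises it by treatment group, and SAP 8.1.5.1 limits the statistical analyses to well-defined profiles. What is missing is a link from %AUCex to the slope and to Rp(AUC).

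Finally, the documents give no quantification limit, so they cannot show that low doses drop out earlier for that reason.

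**Conclusion.** The point holds conditionally. AUC(0-t) is a poor proportionality measure for a drug with a half-life of about 90 h, it is not a declared Part 1 proportionality endpoint, and the dose levels were probably not all sampled equally. If some stopped at 120 h and others at 360 h, the ratio between them is 1.55; it runs from 1.0 to 2.2 for earlier stops from 360 h back to 72 h. The slope shift at 120 h is about +0.05 (800 mg alone late) or +0.10 (640 mg too), roughly half to twice the approximate 95% half-width of 0.05 to 0.10, depending on CV and on which levels ran late.

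Two stronger readings are not supported. One is that the 800 mg AUC(0-t) is inflated: at 360 h it still captures only about 94% of AUC(0-inf), and it is the shorter profiles that would be truncated. The other is that the artefact will be reported as non-proportionality. The SAP sets no proportionality limit, and an upward shift could equally mask less-than-proportional exposure.

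**What to change.** - In Table 4.4, replace AUC(0-t) with a partial AUC from zero to the last nominal sampling time common to all seven Part 1 dose levels. This is AUC(0-120) if the shortest schedule ended there.
- State in the SAP the actual last nominal sampling time for each Part 1 dose level.
- Show the already-planned %AUCex summary by dose beside the AUC(0-inf) slope and beside Rp(AUC), which also rests on AUC(0-inf).
- Do not restrict AUC(0-inf) or Rp(AUC) to profiles with %AUCex of 20% or less. Since 2^(−T/t½) ≤ 0.2 requires t½ ≤ T·ln 2/ln 5, a 120 h profile would qualify only with a half-life below about 52 h, and a 360 h profile below about 155 h. The filter would keep fast eliminators at the truncated doses and nearly everyone at the others. That selects by dose and would bias Rp(AUC) downward.

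The cost is one extra derived parameter from existing samples and a few lines of SAP text. The limitation is that a partial AUC to 120 h covers about 60% of total exposure and says little about dose-dependent terminal elimination, so AUC(0-inf) should stay in the table. If sampling turns out to have been uniform to 360 h, little is lost.
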